10.7 Other safety measurements

10.7.1 Vital signs

Vital signs will be measured within approximately 15 minutes prior to dosing and in addition (pulse and blood pressure only) approximately 30 minutes after dosing with study medication. Study participants should be sitting for at least 5 minutes prior and during the collection of blood pressure and pulse rate measurements. Vital signs are as follows:

- Pulse
- Systolic/diastolic blood pressure measurement
- Temperature

Vital signs will be measured at Screening, Baseline, every visit (including all Unscheduled Visits) through the Early Discontinuation/End of Treatment Visit, and the Final Visit 12 weeks after the last dose of study medication.

10.7.2 Growth (height and weight)

Height will be recorded at Screening, Baseline, every 24 weeks thereafter (for study participants enrolled prior to Protocol Amendment 9, the height assessment will be performed every 48 weeks following Protocol Amendment 8), and the Early Discontinuation/End of Treatment Visit. Height will be recorded after the shoes have been removed. Height should preferably be measured with a wall-mounted stadiometer.

At Screening, change in height and weight over the last 6 months and over the last year will be collected via parent-/self-report, if not available from medical records.

Weight will be recorded after removal of shoes and heavy clothing. Weight will be measured at Screening, Baseline, and every visit through the Early Discontinuation/End of Treatment Visit, and the Final Visit 12 weeks after the last dose of study medication.

Results of the weight measurement will be used to determine the study participant's CZP dose as specified in [Table 7-1](#).

10.7.3 Tanner stages

Assessments of study participants' developmental stages on external genitalia and pubic hair (boys) and on breast and pubic hair (girls) will be performed to determine Tanner stages (Marshall and Tanner, 1969; Marshall and Tanner, 1970). These assessments will be performed at Baseline and every 24 weeks thereafter, and the Early Discontinuation/End of Treatment Visit. For study participants enrolled prior to Protocol Amendment 9, Tanner stages assessment will be performed every 48 weeks following Protocol Amendment 8, and only for those subjects who have not reached Tanner stage V.

10.7.4 Physical examination

Physical examinations (except joint examination) will be performed at Screening, Baseline, Week 4, every visit thereafter through the Early Discontinuation/End of Treatment Visit, and the Final Visit 12 weeks after the last dose of study medication. Physical examination findings will be recorded in the CRF only at Screening. Details of the subsequent physical examinations should be recorded in the source documentation. Clinically relevant changes in subsequent physical examinations will be recorded as AEs.

The following body systems will be examined:

- General appearance
- Ear, nose, and throat
- Eyes
- Hair and skin
- Respiratory
- Cardiovascular
- Gastrointestinal
- Musculoskeletal
- Hepatic
- Neurological
- Mental status

10.7.5 Demographics, JIA history, prior JIA medication, and general medical and procedure history

Demographic data, JIA history including prior medication, general medical and procedure history (including any prior chest radiographs), and concomitant diseases will be recorded by the Investigator at the Screening Visit.

10.7.6 Reproductive potential and birth control

Reproductive potential of all study participants will be assessed by clinical questioning at Screening, Baseline, and every visit thereafter except at Visits 3 and 4 and at Unscheduled Visits. If the study participant is not of reproductive potential, the reason will be recorded (eg, prepubescent, pre-menarcheal). If the study participant is of reproductive potential and is sexually active, the method of birth control used will be recorded. Sexually active study participants (male and female) must use effective contraceptive measures (see Section 6.2, Exclusion Criterion 17).

10.7.7 Pregnancy testing

Pregnancy testing for all postmenarcheal female study participants (regardless of sexual activity) will consist of serum testing at Screening and urine testing at all other applicable visits. For female study participants who start menstruating during the study, urine pregnancy testing will be performed starting at the next applicable visit. Pregnancy testing must be carried out at Screening, Baseline, and every visit thereafter except at Unscheduled Visits (unless deemed necessary by the Investigator).

10.7.8 Autoantibody (ANA and anti-dsDNA antibodies) concentrations

Autoantibodies (ANA and anti-dsDNA antibodies) will be assessed at Baseline (testing for anti-dsDNA antibodies only if ANA is positive), Weeks 16 and 48, and the Early Discontinuation/End of Treatment Visit.

All of these blood draws will coincide with the blood collection times for the assessment of hematology and clinical chemistry parameters, so that no additional blood draws are required.

10.7.9 Assessment and management of TB and TB risk factors

As TNF inhibitors are known to be associated with significant risk of reactivation of LTBI or previously treated active TB, appropriate rigorous precautions are being taken within the protocol (see Section 6.2 [Exclusion Criterion 11] and Section 6.4 [Withdrawal Criterion 2]).

Study participants with known active TB disease, at high risk of acquiring TB infection, or with past or current LTBI or current or history of NTMB infection are excluded from the study.

a. Known TB infection whether present or past is defined as:

- Active TB infection or clinical signs and symptoms strongly suggestive of TB (pulmonary or extra pulmonary).
- History of active TB infection involving any organ system or findings in other organ systems consistent with TB infection.

- Any evidence by radiography or other imaging modalities consistent with previously active TB infection that is not reported in the participant 's medical history.
- b. High risk of acquiring TB infection is defined as:
- Known close exposure (eg, sleeping in the same room) to another person with active TB infection within 3 months prior to Screening.
 - Time spent within 3 months prior to Screening in a healthcare delivery setting or institution where individuals infected with TB are housed or where the risk of transmission of infection is high.
- c. LTBI is defined as an infection by mycobacteria tuberculosis with:
- A positive IGRA (or 2 indeterminate IGRAs), AND
 - Chest imaging (or other imaging) negative for TB infection, AND
 - Absence of signs, symptoms (eg, evidence of organ-specific involvement), or physical findings suggestive of TB infection.
- d. Pulmonary NTMB infection is defined as a group of lung infections caused by mycobacteria different from mycobacterium tuberculosis infections.

10.7.9.1 Physical examination

The investigator should consider all potential sites of infection when assessing for TB during the physical examination and other evaluations and based on the study participant's medical or social history.

The most common primary focus of TB is the lung. Other sites may include gastrointestinal system, bones/joints, lymph glands and meninges etc. However, in immune compromised patients and/or patients treated with TNF inhibitors, extra-pulmonary manifestations of TB are common compared to normal population.

Some common symptoms that the study participant may present are dependent on the primary focus of infection and may include cough, blood in sputum, night sweats, lymphadenitis, joint pain/swelling, spinal deformity, headache/confusion, abdominal pain (mimicking IBD) etc. Unusual presentations should always be considered.

10.7.9.2 IGRA test conversion

Tuberculosis test conversion is defined as a positive or indeterminate (and confirmed indeterminate on repeat) IGRA result for the current test when previous IGRA test results were negative. All study participants with positive or indeterminate IGRA test results must immediately stop IMP administration. In case of an IGRA test conversion, the study participant must be considered as having either a suspected new latent or an active TB infection and be promptly referred to an appropriate specialist (eg, pulmonologist, infectious disease specialist) for further evaluation. Additional assessments (eg, blood tests or IGRA, chest X-rays, or other imaging) should be performed where medically relevant and documented. Such conversions should be reported as AEs as described in the protocol. The AE term would need to be updated with final diagnosis once available.

10.7.9.3 Latent TB infection

In case the evaluation by the appropriate specialist diagnoses a new LTBI, the study participant must permanently stop IMP and be withdrawn from the study. A TB prophylactic therapy in accordance with applicable clinical guidelines might be initiated, if considered appropriate.

Once withdrawn from study treatment, study participants should return for the Early Discontinuation Visit and complete all early discontinuation assessments, and complete an Final Visit (12 weeks after the last dose of IMP). LTBI must be reported as an AE. Follow-up reports should be completed as per protocol requirement until such time as the LTBI resolves.

10.7.9.4 Active TB or NTMB infection

Study participants who develop active TB or NTMB infection during the study must be withdrawn from the study. The study participant must be immediately discontinued from study medication and an Early Discontinuation Visit must be scheduled as soon as possible, but no later than the next scheduled visit. The study participant should be encouraged to keep the Final Visit as specified by the protocol. Treatment should be started immediately.

Note that study participants with history of or active NTMB infection are excluded from the study regardless of prior or current therapy for this condition.

Confirmed active TB is always considered an SAE. UCB's process requires that these must be captured on an SAE report form and provided to the Sponsor in accordance with SAE reporting requirements. Follow-up reports should be completed as per protocol requirement until such time as the TB infection resolves.

10.7.9.5 TB assessment by IGRA or tuberculin skin test (TST)

During the Screening Period, the TB assessment by IGRA will be performed for all study participants (17 years and under). The IGRA (QuantiFERON[®]-TB GOLD In-Tube test) is the protocol-required method of screening for TB. A UCB validated central laboratory shall be responsible for interpreting the results of IGRA. The central laboratory must provide UCB with all assay values (both measured and calculated) in accordance with the approved test label or package insert. The IGRA negative result is as defined by the kit's manufacturer. If a central laboratory is not easily accessible for IGRA, UCB will determine whether the test should be performed by a qualified local laboratory.

If the result of the IGRA test is indeterminate, the test may be repeated once. If positive or indeterminate on retest, the study participant may not be enrolled. The retest must be done during the protocol-defined Screening window.

For study participants 6 to 17 years of age, the TST is optional in some regions/locations, based on local guidelines or requirements taking into account the prevalence of TB in such countries.

In countries with high *bacillus Calmette-Guerin* (BCG) vaccination or high TST positivity, it is not recommended to do the TST. The TST may be positive due to BCG vaccination. UCB will not permit enrollment of pediatric study participants without advice from physician with expertise in pediatric TB.

A positive TST is defined as an induration of ≥ 5 mm occurring 48 to 72 hours after intradermal injection with 5 tuberculin units (TU) of either TST-S or 2TU of TST-RT23. The test must be performed and read by a TST qualified health care professional (per local guidelines). The exact measurement of the observed induration (in mm) must be documented in the study participant's medical record at the same time that it is read. Documentation must include the date and time the test was performed, the testing field (site), and the date and time the test was read.

During the conduct of the study, the TB assessment by IGRA can be repeated at the investigator's discretion. The TST test should not be repeated during the conduct of the study. The test results will be reported as positive, negative, or indeterminate and must be reviewed by an experienced TB specialist, radiologist, or a pulmonologist. If the assessment by IGRA is positive or indeterminate on retest, the study participant must undergo appropriate study-specified withdrawal procedures. The retest during Screening must be done during the protocol-defined Screening window.

10.7.9.6 TB assessment by chest x-ray

Chest radiographic imaging is done at Screening and results must be available at Baseline before first drug administration, unless a chest x-ray or CT is available within 2 months prior to Screening. The chest x-ray must be clear of signs of TB infection (previous or current) before first study medication administration. The chest x-ray should be repeated only if the TB test was confirmed positive or any further evidence is suggestive of potential TB infection (eg, exposure). Radiographic findings suggestive of inactive TB or active TB may include but are not limited to: apical fibrosis, pleural thickening, pulmonary nodules, fibrotic scars, calcified granulomas, upper lobe infiltrates, cavitations and pleural effusions, calcified lung nodules, calcified hilar lymph nodes, and pericardial calcification.

The chest imaging must be negative for old or recent TB infection as determined by a qualified radiologist and/or pulmonary physician. Any new clinically significant findings post Baseline on chest x-ray must be documented in the source documents and the eCRF as an AE.

10.7.9.7 TB risk factors via the TB questionnaire

The TB questionnaire "Evaluation of signs and symptoms of tuberculosis" should be completed accurately and filed as a critical source document. The questionnaire will assist with the identification of study participants who may require therapy for TB. It will be completed as outlined in the schedule of assessments (Table 5-1).

A "Yes" response to any of the questions in the TB questionnaire during the study should trigger further assessments to determine if the study participant has either LTBI or active TB infection and must be withdrawn from the study (see below for details). As an example, a study participant who answers "Yes" at Screening to the question "Has the participant been in close (eg, sleeping in the same room) contact with an individual with active TB, or an individual who has recently been treated for TB?" should not be allowed in the study pending further assessments (including TB specialist consult) to determine if the study participant has either LTBI or active TB infection. In case of any doubt, UCB recommends seeking the opinion of a TB specialist before starting or continuing study medication intake.

10.7.9.8 TB management

For inclusion in the study, see Section 6.2 (Exclusion Criteria).

10.7.9.8.1 Latent TB, active TB, or other NTMB infection identified during study

During the study, study participants who develop evidence of LTBI, active TB, or NTMB infection must immediately stop further administration of study medication and will be referred to an appropriate TB specialist (pulmonologist or infectious disease specialist) for further evaluation and appropriate clinical management. Study participants must be withdrawn and scheduled to return for the Early Discontinuation Visit as soon as possible but no later than the next scheduled study visit and complete all Early Discontinuation Visit assessments. The study participant should be encouraged to complete the Final Visit (12 weeks after the last dose of IMP).

If infection with NTMB is identified during the study, the same procedure as for active TB acquired during the study and compliant TB treatment shall be followed.

10.7.9.8.2 Tuberculosis testing during the study for study participants above and below 5 years of age

Upon signing the updated Informed Consent form, all study participants need to undergo TB testing as described below.

Study participants above 5 years of age

IGRA testing (QuantiFERON) should be done once a year (approximately every 48 weeks) for all study participants from 5 to 17 years of age as described in Section 10.7.9.5.

Study participants below 5 years of age

At Screening, the TST and IGRA are both mandatory. Both these tests must be negative to be eligible for study inclusion (Note that some antihistaminics have the potential to interact with the TST response and render it negative). If either test is positive, the study participant should be referred to a TB specialist and the study participant must not initiate IMP. If the IGRA becomes positive during the study, the IMP administration must be stopped and study participants should be referred to TB specialist.

In countries with high BCG vaccination or high TST positivity, it is not recommended to do the TST. The TST may be positive due to BCG vaccination, however UCB will not permit enrollment of pediatric study participants <5 years of age into a study without written approval from a physician with expertise in pediatric TB.

IGRA testing (QuantiFERON) should be done once a year (approximately every 48 weeks) for all study participants below 5 years of age. There is currently no IGRA adapted to pediatrics in terms of blood volume required for the test (ie, no validated test performance with a smaller blood volume). Therefore, if a maximum cumulative blood draw volume is cited by an IRB/EC for a pediatric clinical study, exceptions may be made for other clinical lab assessments in order to accommodate the IGRA volume requirement.

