- ^k At Screening, laboratory testing includes testing for hepatitis B core antibody, hepatitis B surface antibody, hepatitis B surface antigen, hepatitis C virus antibody, and HIV 1/2. Study participants with a positive hepatitis B virus test will not be allowed in the study (except for anti-hepatitis B surface positive only, in case study participant is immune due to well-documented hepatitis B vaccination or isolated false-positive anti-hepatitis B core test confirmed with a confirmatory test such as hepatitis B virus deoxyribonucleic acid [DNA]). A positive hepatitis C antibody test will be confirmed by a confirmatory test (such as hepatitis C virus ribonucleic acid [RNA]) and those with a positive confirmatory test will not be allowed in the study.
- ^l At Baseline, hematology/chemistry/urinalysis only need to be done if in the Investigator's opinion there is a change in the study participant's status compared to the Screening Visit.
- ^m Pregnancy testing for postmenarcheal female study participants. Serum testing by a central laboratory at Screening and urine testing locally at the site at Baseline, Weeks 8, 16, 24, and every visit thereafter.
- ⁿ TB screening: Interferon-gamma release assay (IGRA) testing (QuantiFERON[®]) is required to be performed by the central lab for all study participants from 5 to 17 years of age. TST and IGRA testing at Screening is mandatory for study participants less than 5 years of age in this study unless written documentation of BCG vaccination is available (refer to [Section 6.2](#) [exclusion criterion 11] and [Section 10.7.9](#)). Following implementation of Protocol Amendment 7, IGRA testing (QuantiFERON) should be done once a year (approximately every 48 weeks) for all study participants.
- ^o Chest radiographic imaging is done at Screening and results must be available at Baseline before first drug administration, unless a chest x-ray or CT is available within 2 months prior to Screening.
- ^p Clinical remission on medication will be assessed at every post-Baseline visit from Week 24 onwards only.

Table 5-1 Schedule of study assessments

| Study period | Screening | Baseline | | | | | | | |
|----------------------------------|------------------------|----------|---|---|---|--|--------------------------------|------------------------------------|-------------------------------|

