| Biologic DMARDs | Any dose | Prior or current exposure to more than 2 biologic DMARDs and/or primary failure (defined as a complete lack of response) to more than 1 TNF inhibitor. Use of anakinra or rilonacept within 7 days prior to the Baseline arthritis assessment. Use of etanercept within 28 days prior to the Baseline arthritis assessment. Use of adalimumab within 56 days prior to the Baseline arthritis assessment. Use of infliximab or abatacept within 60 days prior to the Baseline arthritis assessment. Use of rituximab within 180 days prior to the Baseline arthritis assessment. Use of any other biological response modifier therapy (eg, tocilizumab, canakinumab) within 90 days or 5 half-lives prior to the Baseline arthritis assessment, whichever is longer. (All aforementioned drugs are prohibited during the study.) |

DMARDs=disease-modifying antirheumatic drugs; ia=intra-articular; im=intramuscular; iv=intravenous;
JIA=juvenile idiopathic arthritis; TNF=tumor necrosis factor

7. Study participant has a history of systemic JIA, with or without systemic features.
8. Study participant has a secondary, noninflammatory type of rheumatic disease or of joint pains (eg, fibromyalgia) that in the Investigator's opinion is symptomatic enough to interfere with evaluation of the effect of study medication.
9. Study participant has other inflammatory arthritis (eg, systemic lupus erythematosus, inflammatory bowel disease-related).
10. Study participant has active uveitis or a history of active uveitis within the preceding 6 months.
11. Participant has:
 - a. Known active TB disease
 - b. History of active TB involving any organ system
 - c. History of or current latent tuberculosis infection (LTBI)
 - d. High risk of exposure to TB infection
 - e. Current nontuberculous mycobacterial (NTMB) infection or history of NTMB infection. For further information relating to definitions of known active TB, past history of TB, LTBI, high risk of acquiring TB infection and NTMB infection, refer to Section 10.7.9 (Assessment and management of TB and TB risk factors).

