8.1 Visit 1 (Week -4 to 0) Screening

Prior to any study activities and at least 4 days prior to the Baseline Visit (Visit 2), study participants and parent(s)/legal representative, as applicable, will be asked to read and sign an Informed Consent/Assent Form that has been approved by an IRB/IEC and which complies with regulatory requirements. Study participants and parent(s)/legal representative will be given adequate time to consider any information concerning the study given to them by the Investigator or designee. As part of the informed consent procedure, study participants and

parent(s)/legal representative will be given the opportunity to ask the Investigator any questions regarding potential risks and benefits of participation in the study.

Assessments at this visit will include:

- Obtain written informed consent/assent
- Assessment of inclusion/exclusion criteria
- Demographic data including date of birth, gender, and race/ethnicity
- JIA history and prior JIA medication
- Review of general medical and procedure history, concomitant diseases, and previous and concomitant medications
- Vital signs
- Height*
- Weight*
- Physical examination
- TB questionnaire
- Hematology/biochemistry/urinalysis (including hepatitis and HIV testing)
- Reproductive potential and birth control
- Pregnancy (serum) test for postmenarcheal females
- CRP
- Chest radiographic imaging and results must be available at Baseline before first IMP administration unless a chest X-ray or CT scan is available from 2 months prior to Screening.
- TB screening: TST and IGRA for study participants from 2 to 4 years of age (unless the study participant is located in a country with high TST positivity and/or written documentation for BCG vaccination is available) or IGRA (to be performed by the central lab) for study participants from 5 to 17 years of age. Note that the TST may be positive due to BCG vaccination, however, UCB will not permit enrollment of pediatric study participants <5 years old into the study without written approval from a physician with expertise in pediatric TB**
- TB questionnaire (study participant and parent/caregiver)**
- PRINTO/PRCSG standard joint examination
- Physician's Global Assessment of Disease Activity (VAS)
- CHAQ-parent reported
- Parent's Assessment of Arthritis Pain (VAS)
- Parent's Global Assessment of Overall Well-Being (VAS)

- Adverse events
- IXRS contact (to register study participant with unique study participant number)

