A qualified central laboratory capable of handling small sample/tube sizes will be used in this study. The planned total blood volumes collected at a single time point (visit) will vary between 2mL and 9mL. The highest blood sampling frequency will occur during the first 4 weeks of the study. The maximum total volume collected during this period will be approximately 24mL (at the first 4 study visits).

In addition, treatment of the venipuncture site with an anesthetic cream prior to blood sampling is permitted.

The TB assessment by IGRA testing is required to be performed by the central lab; additional blood sampling of approximately 3mL will be required at Screening.

If the result of the IGRA test is indeterminate, the test may be repeated once. If positive or indeterminate on retest, the study participant must not be enrolled (Section 10.7.9.5).

For study participants from 2 to 4 years of age, TST and IGRA testing will be performed (except for study participants with documented BCG vaccination) as described in Section 10.7.9.8.2. In countries with high BCG vaccination or high TST positivity, only IGRA should be performed (Section 10.7.9.8.2). The TST may be positive due to BCG vaccination, however, UCB will not permit enrollment of pediatric study participants <5 years old into the study without written approval from a physician with expertise in pediatric TB. IGRA testing should be done once a year (approximately every 48 weeks) for all study participants.

The central laboratory will analyze and assess blood and urine samples for the following (except dip stick test and urine pregnancy test); other PK assessments may be periodically performed as per Section 9:

Table 10-2 Laboratory measurements

| Hematology | Serum biochemistry | Urinalysis | | | | | | | | |
|--|--|---|---|--|--|---|-----------------------------------|--------------|----------------------|-------------------------|

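### For children under 5, the protocol gives conflicting Screening rules on whether documented BCG vaccination removes the TST, and three of the four places are worded so that it removes the IGRA too

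*Protocol*

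**What the plan says.** Five places in the current protocol govern TB testing at Screening for the youngest children.

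- **Section 10.7.9.8.2** sets the strictest rule for those under 5: "At Screening, the TST and IGRA are both mandatory. Both these tests must be negative to be eligible for study inclusion". It adds a consequence: "If either test is positive, the study participant should be referred to a TB specialist and the study participant must not initiate IMP". It then advises against the TST in countries where BCG use or TST positivity is high. It has no exception tied to the child's own vaccination record.
- **Table 5-1 footnote n** takes the two tests together and says of the pair that it "is mandatory for study participants less than 5 years of age in this study unless written documentation of BCG vaccination is available".
- **Section 8.1** lists TST and IGRA for ages 2 to 4, "unless the study participant is located in a country with high TST positivity and/or written documentation for BCG vaccination is available".
- **Section 10.6** says that for ages 2 to 4 "TST and IGRA testing will be performed (except for study participants with documented BCG vaccination"), and refers to Section 10.7.9.8.2 for the procedure. Its next sentence reads: "In countries with high BCG vaccination or high TST positivity, only IGRA should be performed".
- **Section 10.7.9.5** says that during Screening "the TB assessment by IGRA will be performed for all study participants (17 years and under"), with no BCG exception.

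Sections 8.1, 10.6 and 10.7.9.8.2 also require written approval from a physician with pediatric TB expertise before any child under 5 is enrolled.

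**The concern.** These are operative instructions that decide what is done before the first dose of a TNF inhibitor in the youngest participants. Section 10.7.9 itself names reactivation of latent TB as a significant risk of the class. A site that works from the schedule, the visit list or the laboratory section would skip the TST in a BCG-documented child. If it took the wording literally, it would skip the IGRA as well. A site that works from Section 10.7.9.8.2 would do both tests and require both to be negative. The same child could therefore be screened differently at two sites, and a missing TST would be a deviation under one section and correct conduct under the others.

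**Working it through.** No arithmetic applies. The check sets the current rules side by side for a child under 5 at Screening.

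| Place | Tests named | Documented-BCG exception | Country exception |
|---|---|---|---|
| Table 5-1 footnote n | TST and IGRA | Yes, attached to both tests | None |
| 8.1 | TST and IGRA | Yes, attached to both tests | Yes (TST positivity only), attached to both tests |
| 10.6 | TST and IGRA, as in 10.7.9.8.2 | Yes, attached to both tests | Yes, IGRA kept |
| 10.7.9.5 | IGRA for all | None | TST not recommended |
| 10.7.9.8.2 | TST and IGRA, both negative | None | TST not recommended |

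**Step 1, the IGRA.** Footnote n, 8.1 and 10.6 make TST and IGRA a single item and hang the exception on the pair, so the literal result is that a BCG-documented child under 5 has neither test. Sections 10.7.9.5 and 10.7.9.8.2 contain no such waiver, and the country sentence in 10.6 keeps the IGRA expressly. Read as a whole, the protocol intends an IGRA for every child. The three sentences are wrong as worded, but the intent can be recovered.

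**Step 2, the TST where BCG use or TST positivity is high.** Section 10.7.9.8.2 advises against the TST there, and the other places waive it for a BCG-documented child. The practical result is the same.

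**Step 3, the TST elsewhere.** For a BCG-documented child under 5 in any other country, the TST is required in 1 place (10.7.9.8.2) and waived in 3 (footnote n, 8.1, 10.6). Two routes to reconciling them fail:
- The individual exception cannot be folded into the country one, because 8.1 joins them with and/or and so treats them as separate grounds.
- The cross-reference does not help, because 10.6 points to 10.7.9.8.2, which has no documented-BCG exception.

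The text gives no order of precedence between the sections.

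**Step 4, who can still be affected.** Section 5.1.2 says that recruitment under all amendments before Amendment 9 is complete and that 30 further participants will be enrolled. The number under 5 is not given, nor is the number with documented BCG or the TB classification of their countries. The affected count therefore lies between 0 and 30 and cannot be narrowed from the protocol.

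**The case against.** The best defence is that the three places a site uses day to day agree with one another on documented BCG. A general rule in 10.7.9.8.2 with a specific exception elsewhere would then be a natural reading. The safeguards are also real: the IGRA is required of everyone in 10.7.9.5, and no child under 5 enters without written expert approval, whichever reading is followed. The affected group may even be empty.

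The safeguards stand and keep the point minor. The general-rule reading does not remove the conflict. Section 10.7.9.8.2 is itself the specific rule for this age group, states its own exception by country, and makes two negative tests a condition of inclusion. Expert approval does not tell a site whether a TST has to be done.

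A reader might infer two stronger points. The documents support neither.

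- *That the protocol means to enrol BCG-vaccinated children with no TB test at all.* The literal wording of the three exceptions gives that result, but 10.7.9.5, 10.7.9.8.2 and the country sentence in 10.6 show that it is not the intent.
- *That a TST-positive, IGRA-negative child may be enrolled because exclusion criterion 11 is silent.* Criterion 11 lists "History of or current latent tuberculosis infection (LTBI"), the LTBI definition in Section 10.7.9 rests on the IGRA, and no TST result is named. But 10.7.9.8.2 bars such a child from treatment, nothing contradicts that bar, and footnote n, 8.1 and 10.6 all lead the reader to Section 10.7.9 or directly to 10.7.9.8.2. A rule stated once and contradicted nowhere is binding. Its absence from criterion 11 is not an error.

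**Conclusion.** The contradiction is real and narrow. For BCG-documented children under 5 outside countries with high BCG use or TST positivity, the Screening TST is both required and waived. In addition, three sentences are worded so that they waive an IGRA that the protocol requires elsewhere.

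Severity is minor. The conclusion rests on the current text alone and needs no assumption about how sites behave. Its practical reach does depend on how many Amendment 9 enrollees are under 5 with documented BCG, which is not stated. No endpoint, analysis set, sample size or estimate changes.

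**What to change.** Use one rule, worded identically, in Table 5-1 footnote n, Section 8.1, Section 10.6 and Section 10.7.9.8.2:

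- An IGRA is done at Screening for every participant and is never waived.
- Under 5 years, a TST is done as well.
- Any exception, whether for documented BCG or by country, applies to the TST only.

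The sponsor, with its TB experts, decides once whether the documented-BCG exception stays.

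As an optional clarification, exclusion criterion 11 could repeat the bar already in 10.7.9.8.2: under 5 years, a positive TST, where one is done, excludes. It could add that written specialist approval is an additional requirement and does not override a positive result.

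The cost is wording in four places (five with the clarification) and a memo to sites. Keeping the documented-BCG exception adds no test beyond the IGRA that 10.7.9.5 already requires. Deleting it means one TST, read at 48 to 72 hours, for BCG-documented children under 5 outside countries where BCG use or TST positivity is high.
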